Peer leaders will receive \$180.00 for each group they co-facilitate. Specifically, they will receive \$60.00 at the end of the third group session and another \$60.00 at the end of the sixth group session they co-facilitate. Peer leaders will receive an additional \$60.00 at the completion of the end of the 8th supervision session. This makes the total compensation for the peer leaders co-facilitating a group \$180.00 per group. In addition, peer leaders will also be asked to participate in either an in-person or online (previously recorded) training for the intervention for which you they are co-leading. If attending in person travel expenses (e.g. train, airfare, ground transportation) will be covered by the research award to host them in New Haven, Connecticut. Lodging and per diem expenses will also be covered by the study for up to 3 days. In addition as a token of our appreciation you they will be compensated \$100.00 per day (maximum 3 days) for their attendance in the training.

Participants will be given a choice regarding how they would like to receive payment: either by postal mail or via e-mail. Checks will be mailed to participants, if this is their preferred method. Electronic gift cards will be e-mailed to those who prefer an e-mail delivery.

3. **Costs for Participation (Economic Considerations):** Clearly describe the participant's costs associated with participation in the research, if any, and the interventions or procedures of the study that will be provided at no cost to participants.

Interventions will be at no cost to the participant. A travel stipend will be provided for peer specialists attending various trainings.

References

Aosved, A. C., Long, P. J., & Voller, E. K. (2011). Sexual revictimization and adjustment in college men. *Psychology of Men & Masculinity*, 12(3), 285-296.

Apodaca, T. R., Borsari, B., Jackson, K. M., Magill, M., Longabaugh, R., Mastroleo, N. R., & Barnett, N. P. (2014). Sustain talk predicts poorer outcomes among mandated college student drinkers receiving a brief motivational intervention. *Psychology of Addictive Behaviors*, 28(3), 631-8.

Badgett, M. V. (1995). The wage effects of sexual orientation discrimination. *ILR Review*, 48(4), 726-39.

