Those participants who meet inclusion criteria will be provided a link to the online surveys for baseline assessment. Measures will include prior and current mental health treatment engagement, barriers and beliefs around seeking formal mental health treatment, as well as measures assessing symptomatology (e.g., substance use, depression, PTSD). At the completion of the 6-week group, participants will complete post-intervention assessments and 60- and 120-day follow-up assessments on the various outcome measures. A summary of the timing and purpose of assessments is shown in Table 1.

Baseline, Post-Intervention and Follow-up Outcomes

Primary Outcome: Mental Health Treatment Engagement. The primary outcome here will be the binary distinction between those who initiated mental health treatment/reinitiated mental health treatment versus those who did not. Mental health treatment engagement will be operationally defined as having ≥ 1 visit(s) or scheduled appointments to any mental health services within 120 days of the last online group.

Primary Outcome: Depression. Center for Epidemiological Studies Depression Scale (CES-D; Radloff, 1977) is a 20-item questionnaire that asks about experience and frequency of depressive symptoms over the past week. A score of 16 or higher identifies those individuals who are at risk for major depression.

Secondary Outcome(s): will include PTSD, alcohol and drug abuse, quality of life, and service utilization.

PTSD Checklist for DSM-5 (PCL-5; Weathers et al., 2013) is a 20-item instrument that corresponds to the current psychiatric diagnostic criteria for PTSD.

Alcohol, Smoking and Substance Involvement Screening Test (ASSIST; WHO ASSIST Working Group, 2002; Humeniuk et al., 2008) is an 8-item measure of participants’ use of alcohol, tobacco products, and other drugs across their lifetime and in the past three months.

Inventory of Psychosocial Functioning (IPF-B; Rodriguez, Holowka, & Marx, 2012) is a brief 7-item scale that assesses functional impairment or quality of life related to trauma and PTSD.

The Service Use and Resource Form (SURF; Rosenheck et al., 2016) is a questionnaire assessing current living situation, use of inpatient and outpatient mental health and alcohol or drug treatments, psychotropic medication use, and use of other support services. The SURF will be administered during screening, baseline, post-intervention and follow-up.

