a. Targeted for enrollment at Yale for this protocol: 356 for the online groups.

b. If this is a multi-site study, give the total number of participants targeted across all sites.

4. How was this estimate derived?

Because this study examines repeated measures outcomes with the two treatment conditions, assigned at the individual level, power analysis makes several assumptions: continuous outcomes, a linear link function, random effects covariance structure, and homogeneous covariance structure (within treatment groups). These analyses also assume testing for HTE effects. Conservatively assuming an effect size of .35, with a power of .80 and an alpha of .05, 137 subjects per group would be required. This represents a total completed sample of 274. Assuming a dropout rate of 20% (rounded up to 70, for nearest multiple of 2), this requires a recruited sample of at least 344. In a meta-analysis of 72 clinical trials, the initial effect size, that is 1-month post-intervention, was quite high ($d = .77$). However, the strength of the effect decreased over time, with effect sizes of .39 at 1-3 months, and .31 at 6-12 months.

5. Process of Consent/Accent (*NOTE: When a study includes minors, parent provide permission [not consent] for the child's participation, and the child provides assent for participation*)

Informed consent is an ongoing process that is best suited by transparency and openness to participants. Thus, participants will give consent in the initial online screening contact form and verbally in the screening call. Participants will be provided with information about the nature of the study, as well as the expected time and energy commitment required to complete the assessments. It will also be explained to participants that they are consenting to be randomly assigned to one of two MI interventions (with brief explanation about content as well as frequency and length of sessions).

Participants will be asked to provide informed consent online, prior to completing in the screening questionnaires. Consent will be required in order to access the assessment measures. If a participant does not provide consent, they will not engage in the screening assessment or be enrolled in the study.

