Webber, K. H., Tate, D. F., Quintiliani, L. M. (2008). Motivational interviewing in internet groups: a pilot

study for weight loss. *J Am Diet Assoc*, 108(6),1029-32.

West, D. H., Harvey, J. R., Kruckowski, R. A., Prewitt, T. E., Priest, J., & Ashikaga, T. (2016). Do individual online motivational interviewing chat sessions enhance weight loss in a group online weight control program? *Obesity*, 24(11), 2234-2340.

Westra, H. A., Aviram, A., & Doell, F. K. (2011). Extending motivational interviewing to the treatment of major mental health problems: Current directions and evidence. *Canadian Journal of Psychiatry*, 56(11): 643-650. Doi: 10.1177/070674371105601102

WHO ASSIST Working Group. (2002). The Alcohol, Smoking and Substance Involvement Screening Test (ASSIST): development, reliability and feasibility. *Addiction*, 97(9), 1183-1194.

Williams, J. K., Kisler, K. A., Glover, D., & Sciolla, A. (2011). *Exploring childhood sexual experiences and vulnerability to intimate partner violence among African American MSMW: Was that abuse or love?* New York: Nova Science Publishers.

Analysis Plan

To assess the success of randomization, baseline demographic and clinical characteristics, the two randomized groups were compared using chi-square tests for categorical variables and t-tests or Mann-Whitney tests for continuous variables. Data analyses were conducted on the intent-to-treat sample. All variables were evaluated for their distributional properties and data processing errors. Robust estimators were used to address non-normal data.

Variables were assessed for amount and pattern of missing data. Full information maximum likelihood estimation was used in subsequent analyses to address missingness. Inclusion of informative variables were included as needed. Analyses were conducted in SPSS 28.0 (IBM, 2021). For outcome analyses, linear mixed models (LMM) of mental health symptoms were modeled as a repeated measures outcome variable, nested within participants. Baseline demographic, clinical variables, and sexual abuse experiences were included as time-invariant covariates (between participants), as was treatment group. Thus, for each outcome, the primary analysis included all observations nested in persons and cohorts, controlling for baseline clinical and demographic variables.

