Before examining the potential role of any mediators, LMM was conducted to determine any main or interaction effects condition and/or time may have had on these mediators as outcomes. To assess heterogeneity of treatment effects, the potential moderating impact that participant demographic variables and significantly correlated covariates had on the relationship between condition and primary outcomes was examined by including a moderator x condition interaction term in models.

Inclusion of demographic and clinical variables in mixed models allowed for testing of heterogeneity of treatment effects (HTE), with adjusted *p*-values. Specifically, in addition to the primary analyses, subsequent supplementary analyses tested potential moderators by including a treatment group X demographic interaction (race, comorbidity, and education) as these are the most likely candidates for HTE effects. Potential moderating effects of baseline values of minority stress, conformity to masculine norms and barriers to help seeking were also examined using SPSS PROCESS, which provides estimates of conditional effects of focal predictor (treatment condition) at different values of the moderator.

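### Two primary outcomes are named, but no analysis is stated for the binary one (treatment engagement), the .80 power does not cover it, and no rule links the two

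*Combined protocol and SAP*

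**What the plan says.** **Outcomes (Section IV, item 3).** Engagement comes first: "The primary outcome here will be the binary distinction between those who initiated mental health treatment/reinitiated mental health treatment versus those who did not". It is met by at least one visit or by "scheduled appointments to any mental health services within 120 days of the last online group", so each participant has one yes/no status. A second entry is headed "Primary Outcome: Depression" and names the CES-D. Secondary outcomes have their own heading. On timing, "participants will complete post-intervention assessments and 60- and 120-day follow-up assessments on the various outcome measures", so the CES-D has three post-baseline values.

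**Model (Analysis Plan).** "For outcome analyses, linear mixed models (LMM) of mental health symptoms were modeled as a repeated measures outcome variable, nested within participants". The same paragraph concludes that "for each outcome, the primary analysis included all observations nested in persons and cohorts, controlling for baseline clinical and demographic variables". Chi-square tests are named only for comparing the arms at baseline. Full information maximum likelihood (FIML) is named for missing data. The moderator analyses refer to the primary outcomes in the plural and add interaction terms to models, but no model for engagement is described.

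**Multiplicity (Analysis Plan).** The only adjustment concerns moderators: including demographic and clinical variables "allowed for testing of heterogeneity of treatment effects (HTE), with adjusted" p-values.

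**Sample size (Section V, item 4).** The "power analysis makes several assumptions: continuous outcomes, a linear link function, random effects covariance structure" and a homogeneous covariance structure. With an effect size of .35, power .80 and alpha .05, it asks for 137 per group. No engagement rate is given.

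**Hypothesis (Section IV, item 1).** The tailored arm is expected to improve engagement and to reduce trauma-related symptoms. The CES-D is not named there.

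**The concern.** Whether tailored MI brings more survivors into formal care is the first-listed question and the purpose of the trial, yet a reader cannot tell from the plan how it is tested. A linear repeated-measures model of symptom scores is not an analysis of one binary status per person, and the stated power was worked out for a different kind of outcome.

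The second gap is the missing link between the primaries. With one positive and one negative result, the trial could be reported as a success or as a failure, and the plan would not contradict either account. The CES-D adds a further choice, because its primary test could be taken at any of three visits or as a time-by-arm contrast.

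**Working it through.** **Inputs from the documents.** Section V, item 4: effect size .35, power .80, alpha .05, 137 per group, 274 completers, 20% dropout, 356 enrolled. Section IV, item 3: groups of 8-10 members.

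**Assumptions, none of them in the documents.** Two-sided tests; control engagement rates of 10% to 70%; intraclass correlation (ICC) of .01 or .05; correlation between the two test statistics of 0, .5 or .8.

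**1. The plan's own figure.** For two means, n = 2 × ((1.960 + 0.842)/.35)² is about 128, so 129 per group, against 137 stated. The number of repeated measures, the within-person correlation and the allowance for heterogeneity tests are not given, so 137 cannot be called wrong. It is slightly conservative: power at 137 is Φ(.35 × √(137/2) − 1.960) = .826. The dropout step does reproduce: 274/.80 = 342.5, so 343, rounded to an even 344. Nothing in this derivation involves a proportion.

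**2. Detectable engagement difference at .80 power.** Solve for p2 − p1 in Φ{[(p2 − p1)√n − 1.960√(2p̄(1 − p̄))] / √(p1(1 − p1) + p2(1 − p2))} = .80, where p̄ is the mean of p1 and p2. For clustering, replace n by n/(1 + (m − 1) × ICC). Since 137 is a count of completers, m must be the analysed group size: 8 × .8 = 6.4 to 10 × .8 = 8.

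| Case | Design effect | Effective n per arm | Detectable difference, control rates 10-70% |
|---|---|---|---|
| Independent | 1 | 137 | 12.4-16.8 points |
| ICC .01, m = 6.4 | 1.054 | 130.0 | 12.8-17.3 |
| ICC .01, m = 8 | 1.07 | 128.0 | 12.9-17.4 |
| ICC .05, m = 6.4 | 1.27 | 107.9 | 14.3-19.0 |
| ICC .05, m = 8 | 1.35 | 101.5 | 14.8-19.6 |

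In the independent case, the values at 10, 20, ..., 70% are 12.4, 15.1, 16.4, 16.8, 16.6, 15.7 and 14.2.

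**3. Can the .80 be carried over to engagement?** That depends on what .35 means for a proportion.
- As an odds ratio, exp(.35 × π/√3) = 1.89. Power with independent participants is .42-.74 at 137 per arm, and .44-.76 at 142 (356/2 × .8 = 142.4).
- At ICC .05 with m of 6.4 to 8, the same odds ratio gives .33-.64 at 137.
- As Cohen's h, Φ(.35 × √(n/2) − 1.960) = .83 at 137 and .84 at 142, with independent participants.

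**4. Consequence of having no rule.**
- Either suffices at .05, both nulls true: 1 − .95² = .0975 at correlation 0. The bivariate normal gives .091 at .5 and .078 at .8.
- Both required, .80 power each: .80 × .80 = .64 at correlation 0, and .69 at .5.
- Both required, CES-D at .80 and engagement on the odds-ratio reading at 137 per arm, correlation 0: .80 × .42 to .80 × .74, or .34-.59, if independent; .80 × .33 to .80 × .64, or .26-.51, at ICC .05.

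**5. Cost of Holm.** An outcome with .80 power at .05 has Φ(1.960 + 0.842 − 2.241) = .71 at the first step (.025).

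**The case against.** **The linear model is limited to symptoms.** A reader might infer that the plan applies a linear mixed model to engagement, because the primary analysis is said to hold for each outcome. The documents do not support that. The sentence concludes a paragraph about mental health symptoms, and its natural reference is to those outcomes. What stands is that the engagement analysis is not stated, although the moderator section presupposes one.

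**Missing data are addressed in part.** FIML is stated for the subsequent analyses, with informative variables added as needed, so the plan is not silent. It remains open whether FIML carries over to a once-per-participant binary outcome.

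**The hypothesis joins the two aims.** If its wording means that both outcomes must succeed, no alpha is lost. That is a fair reading of intent, but the sentence speaks of trauma-related symptoms, does not name the CES-D and sets no success criterion. The error inflation is therefore conditional: it applies only if either primary suffices.

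**The sample may be adequate.** A reader might infer from the detectable differences that the trial is too small for engagement. They do not show this. The documents give no engagement rate, no target difference and no ICC, and one reading of .35 gives power above .80.

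**The analyses are reported as done.** The Analysis Plan is in the past tense, so prospective error control may no longer be recoverable. That affects how the fix must be labelled; it does not remove the need for it.

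**Conclusion.** The point holds as a gap in specification. Two outcomes carry the primary label. The first-listed one has no stated main-effect analysis suited to a single yes/no status, no rule connects the two, and the CES-D has no named time point or contrast. The missing engagement analysis and the missing rule must be fixed. The power point is smaller: the .80 should be restated as belonging to the continuous outcome.

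The family-wise error of .078 to .0975 assumes that either primary suffices at .05 and that the correlation lies between .8 and 0. If both are required, the issue is joint power, .64 to .69 at best-case .80 each and correlation 0 to .5. The engagement figures rest on assumed control rates and ICCs and indicate precision only.

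**What to change.** 1. **Engagement analysis.** Analyse engagement once per participant with a logistic mixed model or a logistic GEE, clustered on cohort (and say whether cohort means the therapy group). Include arm, the treatment-naive/experienced randomisation factor, and the baseline demographic, clinical and abuse-history covariates that the Analysis Plan already names. Report a risk difference with 95% CI. State whether FIML applies to this outcome; if not, use multiple imputation, with missing counted as not engaged as a sensitivity analysis.
2. **Power statement.** Restrict the .80 to the continuous outcome. Give engagement precision separately and label it assumption-based: at 137 completers per arm and control rates of 10-70%, about 12-17 points if participants are independent, about 13-17 at ICC .01 and about 14-20 at ICC .05, with analysed groups of about 6.4 to 8.
3. **Decision rule.** Name the CES-D time point or contrast. Use Holm across the two primaries by default, unless the investigators confirm that the hypothesis means both are required at .05 each.
4. **Timing.** State whether the engagement model and the rule were set before outcomes were seen. If not, label them post hoc and report that prospective error control cannot be claimed.

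**Cost.** Wording and modest analysis work, with no new participants or data. Holm takes an outcome with .80 power at .05 to .71 at its first step. Requiring both makes the chance of success depend on engagement power, which clustering lowers below the independent-participant figures.

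### Treatment engagement and CES-D are both primary, but no rule says whether one or both must succeed; if either may be claimed at an unadjusted two-sided .05, familywise error is about 9–10%

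*Combined protocol and SAP*

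**What the plan says.** Section IV, item 3 (Research Plan), under the baseline, post-intervention and follow-up outcomes, has two headings of equal rank: "Primary Outcome: Mental Health Treatment Engagement" and "Primary Outcome: Depression. Center for Epidemiological Studies Depression Scale". Engagement is a yes/no outcome with a window of 120 days after the last group. CES-D is a scale score measured at baseline and at three later assessments. The Analysis Plan also uses the plural: "relationship between condition and primary outcomes was examined".

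The only alpha is in Section V, item 4, where the sample size is derived "with a power of .80 and an alpha of .05". That calculation assumes "continuous outcomes, a linear link function".

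The Analysis Plan says that "linear mixed models (LMM) of mental health symptoms were modeled as a repeated measures outcome variable". It then describes a single primary analysis for each outcome, which uses every observation, nests observations within persons and cohorts, and adjusts for baseline variables. It names no binary model and no CES-D contrast, and it does not define cohort. Its one multiplicity statement concerns moderators: including covariates "allowed for testing of heterogeneity of treatment effects (HTE), with adjusted" p-values.

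The Analysis Plan is in the past tense ("Analyses were conducted in SPSS 28.0").

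**The concern.** With two primary outcomes, the reader needs to know before the data are seen what counts as a positive trial. The rule could be that either outcome suffices, that both are needed, or that one is tested first. These rules have different error rates and power, and they lead to different conclusions from the same data.

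The documents choose none of them. If CES-D favours the tailored intervention and engagement does not, or the reverse, the trial could be called a success or a failure, and that choice could be made after the results are known. The analysis of each outcome is also left open, because it is not stated which term or time point of the CES-D model carries the claim, or how a yes/no outcome is modelled.

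**Working it through.** **The plan's own figure.** Inputs from Section V, item 4: d = .35, power .80, alpha .05, 137 per group, 274 completers, 344 recruited.

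- Two-sided normal formula: n = 2(1.960 + 0.842)² / .35² = 128.1, so 129 per group (130 with the t distribution). The stated 137 is slightly larger. The plan refers to a repeated-measures model but gives no correlation, so 137 cannot be fully checked and is not shown to be wrong.
- Dropout: 274 / .80 = 342.5, so 343, against 274 + 70 = 344 in the plan. These agree apart from rounding.

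The familywise calculation below does not depend on n.

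**Either outcome may be claimed.** Assumptions, none of them in the documents: one test per primary outcome, each at two-sided .05, and either sufficient for a claim. Under no effect on either outcome:

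P(at least one false claim) = .05 + .05 − P(both reject)

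| Correlation of the two tests (assumed) | P(both reject) | Familywise error |
|---|---|---|
| 0 | .0025 | 1 − .95² = 9.75% |
| .4 | .0068 | 9.3% |
| .6 | .0125 | 8.8% |
| any | at least 0 | at most 10% |

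The figures for non-zero correlation use a bivariate normal distribution. Familywise error falls below 9% only when the correlation exceeds about .5.

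**Both outcomes required.** A false claim then needs a rejection of at least one true null tested at .05, so the error rate stays at or below 5%. Joint power cannot exceed the lower of the two powers. The documents give no power for engagement, so joint power cannot be determined.

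**Holm across two named tests.** The smaller p-value is compared with .025 and, if that is significant, the larger with .05. With no effect on either outcome, the familywise error is the chance that either test passes .025: 4.9%, 4.8% and 4.5% at correlations 0, .4 and .6.

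**What Holm costs CES-D.** Two-sample t-test, d = .35, no covariates, one time point, independent observations:

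| Completers per arm | Power at .05 | Power at .025 |
|---|---|---|
| 137 (Section V, item 4) | 82.3% | 74.0% |
| 142 (356 / 2 × .80) | 83.6% | 75.6% |

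On this basis Holm power for CES-D lies between the two columns: the .025 value if engagement is never significant, and the .05 value if it always is.

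**The case against.** **The hypothesis already joins the two outcomes.** Hypothesis 2 (Section IV, item 1) predicts more engagement and also fewer trauma-related symptoms, which could be read as requiring both. If so, alpha is not inflated. But the sentence does not name CES-D. The Research Plan spreads symptoms over PTSD, depression, drinking and drug use, and the outcomes section makes PTSD and substance use secondary. The wording is a prediction, not a decision rule. What stands is that 9–10% describes one reading of a silent plan. A reader might infer that this trial has a 9–10% false-positive rate; the documents do not establish that.

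**Adjustment is partly a matter of judgement.** In a comparative-effectiveness trial the two outcomes can be treated as separate questions, each reported with its interval. That is defensible, but it is also a rule that has to be stated, and the plan does not state it.

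**Stronger readings that the text does not support.** Because CES-D is measured three times after baseline, a reader might infer that each time point could be claimed separately, with a larger error rate. The Analysis Plan describes one primary analysis per outcome using all observations. It does not exclude the multiple-time-point reading, but it makes it speculative. A reader might also infer that engagement has no planned analysis, or that clustering is ignored. The per-outcome wording arguably covers engagement, and nesting in cohorts may already cover the online groups. The narrower point is that no binary model is specified and cohort is undefined.

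**The power cost may be overstated.** The t-test ignores baseline adjustment and repeated measures. With an assumed baseline correlation of .5, power at .025 and 137 per arm is about 86%. Clustering within groups works the other way. Both qualifications stand, so the table is a simple reference and not a forecast.

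**Conclusion.** The concern holds as a missing decision rule. Two outcomes are labelled primary, and nothing in the documents ranks them, says how many must succeed, or adjusts between them. Confidence in that omission is high.

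The size is conditional. With one two-sided .05 test per outcome and either claimable, familywise error is 9.75% under independence, 9.3% and 8.8% at assumed correlations of .4 and .6, and at most 10%. With both required there is no inflation, and the gap is the absent power calculation for engagement.

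The omission affects how the main result may be claimed. It does not invalidate the data. The sponsor should correct it.

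**What to change.** 1. Name one test and one p-value per primary outcome: a single CES-D contrast from the mixed model (for example the difference between conditions at 120 days, which matches the engagement window) and a binary model for engagement. Keep the planned nesting in both and state whether cohort means the online group or a wave of groups.
2. Apply Holm across the two at an overall two-sided .05. Claim Hypothesis 2 only for the outcome or outcomes significant after adjustment, and report both with confidence intervals whatever the result.
3. If both were meant to be required, state that instead and add a power calculation for engagement with its assumed rates.
4. Because the Analysis Plan reads as already carried out, establish whether outcome data had been seen. If so, disclose that no rule was prespecified and label both the contrast and the adjustment as post hoc. Holm cannot restore prespecification.

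The cost is one paragraph in the protocol and Analysis Plan and no extra participants. On the simple t-test, the .025 first step costs CES-D about 8 percentage points of power (82% to 74% at 137 per arm, 84% to 76% at 142). That is the most Holm can cost on that basis, and the loss is smaller when engagement is itself significant. Baseline adjustment and repeated measures would raise these power figures, and clustering would lower them.
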